3. STUDY DESIGN

3.1 Overall Study Design

This is a Phase II, randomized, double-blind, placebo-controlled study to assess the efficacy, tolerability, and safety of MT-7117 in subjects with EPP. The study consists of a 2-week screening period, a 16-week double-blind treatment period, and a 6-week follow-up period at Week 22. The total participation period is approximately 24 weeks.

This study is being conducted without regard to seasonality.

The study design is illustrated in Figure 3.1-1.

Subjects will attend Screening (Visit 1) up to 2 weeks before Randomization (Visit 2), in order to confirm eligibility and obtain pre-study safety assessments including nevi evaluation. Subjects will also be instructed how to use a sunlight exposure diary.

At Visit 2, subjects meeting eligibility criteria will be randomized in a 1:1:1 ratio to receive either [REDACTED], [REDACTED] of MT-7117, or matching placebo in a double-blind manner. Baseline average daily sunlight exposure time without prodromal symptoms (≤ 30 min and >30 min) will be used as stratum for the randomization. The first dose will be administered at Visit 2 following baseline assessment including in-clinic sunlight exposure test. Active or placebo [REDACTED] will be administered once daily in the morning with food.

Subjects will attend in-clinic visits at Weeks 4, 8, and 12 (Visits 5, 6, and 7, respectively) during which assessments will be performed. In addition, subjects will undergo mobile laboratory sample collection at Weeks 1 and 2 (Visits 3 and 4, respectively) to measure liver function markers (AST, ALT, GGT, ALP, direct and total bilirubin).

Subjects will attend the end of treatment visit at Week 16 or early termination (Visit 8). Following the last treatment visit, subjects will attend a follow-up visit at Week 22 or 6 weeks after early termination.

[figure not shown]

Figure 3.1-1 Study Design Schematic

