3.2 Rationale for Study Design and Treatment Regimens

The objectives of this study are to obtain efficacy, tolerability, and safety data for the selected two doses (██████ and ██████ day) of MT-7117 and placebo when administered to subjects with EPP over a 16-week treatment period. A standard randomized, placebo controlled, double-blind treatment allocation is considered appropriate in order to obtain unbiased results in this study. Safety and PK/pharmacodynamic effects will be evaluated based upon these comparable data from the Phase I, MT-7117-E01 study.

Abnormal biochemical parameters related to the hepatic function were observed in rats and monkeys. In MT-7117-E01 human study, in subjects receiving 14 days of study drug, treatment emergent transaminase elevations were reported in 6/36 (17%) subjects receiving MT-7117 and 2/12 (17%) subjects receiving placebo. Of the six subjects receiving MT-7117 for 14 days reporting treatment emergent transaminase elevations, 4 had elevated baseline transaminase values. Therefore, frequent assessments of liver function markers are performed in this study.

The 16-week treatment period is considered a sufficient duration for evaluation of the efficacy and tolerability of MT-7117 for this study. Subjects will attend a follow-up visit 6 weeks after the end of treatment (or early termination) which is considered a sufficient duration to evaluate pigmentation recovery and safety of subjects. For the primary and secondary endpoints, the effect of MT-7117 on the duration of sunlight exposure will be measured using a sunlight exposure diary. Melanin density assessments are safe and routinely used in clinical studies of skin disorders and will be used in this study to assess the effect of MT-7117 on pigmentation. The effect of MT-7117 on quality of life will be assessed using questionnaires. The exit interview questionnaire will measure the clinical

Mitsubishi Tanabe Pharma Development America, Inc.

benefit of MT-7117 and perspectives of quality of life.

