8. ADVERSE EVENT MANAGEMENT

All AEs and SAEs will be recorded in the source documents. All AEs and SAEs that occur from the time written informed consent is obtained until the end of the follow-up period (6 weeks after the last treatment visit, for safety monitoring) will be recorded in the eCRF.

ICF signing will occur weeks in advance of the first clinic visit (Visit 1), to account for subjects traveling long distances; these subjects will be required to sign the ICF before he or she travels to the clinic. In addition, there will be a provision for a pre-screening ICF in order to enable Visit 1 to align directly with the official study consent; however, the Sponsor safety team will determine when to officially collect AE.

Even if the AE is assessed by the Investigator as not related to study medication, its occurrence must be recorded in the source documents and eCRF. AEs will be classified as occurring at 'Baseline' if they occur before the administration of study medication. AEs will be classified as 'treatment-emergent' if they arise following the first administration of study medication in the double-blind treatment period (after randomization) or if a pre-dose AE increases in severity following dosing in the double-blind treatment period (after randomization).

At each study visit, after the subject has had an opportunity to spontaneously mention any problems, the Investigator or designee should inquire about the occurrence of AEs. The questioning should be open-ended and non-leading to avoid notifying either the subject or study site personnel of the actual treatment being administered.

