8.7 Recording and Reporting of Adverse Events

All AEs, regardless of the relationship to study medication, occurring from the time written informed consent is obtained from a subject until the end of the safety follow-up period or the withdrawal of the subject from the study, and any AEs or SAEs reported spontaneously through the end of the safety follow-up period, should be reported to the Sponsor or designee.

NOTE: elective hospitalization or procedure/surgery planned before subject enrollment for a preexisting medical condition does not constitute an AE unless the underlying disease or condition worsens after signing informed consent.

At each study visit, after the subject has had an opportunity to spontaneously mention any problems, the Investigator should inquire about the occurrence of AEs. The questioning will be open-ended and non-leading.

All AEs will be recorded in the source documents and AE eCRF. The AE eCRF will contain a description of the event, date of onset, date of resolution, severity, treatment required, relationship to study medication, action taken with the study medication, outcome, and whether the event is classified as serious.

The Investigator will evaluate the severity of the AEs (as defined in Section 8.3) and will assess the causality between the AEs and the study medication (as defined in Section 8.5).

Pre-existing illnesses, which started before entry and is still ongoing at the start of the study, will not be considered AEs unless they worsen during the treatment period. Pre-existing conditions will be recorded as medical history.

If the Investigator becomes aware of any new safety information, or any safety information which appears to be either study or study medication related after the final follow-up period, then they must notify the Sponsor or the designee immediately.

8.8 Recording and Reporting of Serious Adverse Events or Hepatic Adverse Events of Special Interest

All SAEs and Hepatic AESI occurring from the time written informed consent is obtained from a subject until the end of the safety Follow-up period or the withdrawal of the subject from the study must be reported to the Sponsor or the designee using the *Serious Adverse Event/Adverse Event of Special Interest (SAE/AESI) in a Clinical Study Form* within 24 hours of the Investigator becoming aware of the SAE/AESI. All SAE/AESIs must also be entered in the AE section of the eCRF within 24 hours.

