## 7.12 Safety Assessments

### 7.12.1 Adverse Events

The treatment emergent adverse events (TEAEs) are defined as AEs that newly occurred or increased in severity on or after the first dose of study medication.

The hepatic AEs will be selected from available TEAEs reviewed by the Clinical and Drug safety team. Then Clinical and Drug safety team will provide a list of hepatic AEs in Excel format to Data Science team. The list on Excel format will be used with clinical database to generate the hepatic AE table and listing.

The TEAEs are summarized for subjects with at least one TEAE, at least one treatment emergent adverse reaction, at least one serious TEAE, at least one serious treatment emergent adverse reaction, at least one TEAE leading to drug withdrawn, at least one treatment emergent adverse reaction leading to drug withdrawn, at least one hepatic AE, at least one Adverse Events of Special Interest (AESI) and fatal TEAE.

The frequency and incidence of TEAEs will be summarized by System Organ Class (SOC) and Preferred Term (PT) by treatment and overall. For this table, SOC is sorted by International order; then within SOC, PT is sorted by descending counts under MT-7117

Total group, then descending counts under Placebo group, then alphabetic order for PTs with the same count.

The AE summaries will be presented for the following:

- TEAEs by SOC and PT
- TEAEs by SOC, PT and severity
- TEAEs by SOC, PT and relationship
- Treatment emergent adverse reactions by SOC and PT
- Treatment emergent adverse reactions by SOC, PT and severity
- Serious TEAEs by SOC and PT
- Serious treatment emergent adverse reactions by SOC and PT
- TEAEs leading to drug withdrawn by SOC and PT
- TEAEs by SOC and PT for TEAEs with frequency  $\geq 3\%$  in total MT-7117 group
- Treatment Emergent Hepatic AEs by SOC and PT

For each of the summaries will be done at the subject level - multiple occurrences of the same event within a subject will be counted once in the summaries by SOC and PT; multiple occurrences of the same event within a subject will be counted once in the maximum intensity category (severe > moderate > mild) and/or maximum drug relationship category (reasonable possibility, no reasonable possibility). If intensity or relationship is found to be missing the most severe occurrence will be imputed for that particular summary.

All AEs for each subject, including multiple occurrences of the same event, will be listed.

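### Protocol 8.7 counts worsening of a pre-existing illness as an adverse event only during the treatment period, which conflicts with AE collection from consent to the end of the 6-week follow-up and with the SAP's open-ended TEAE definition

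*Protocol*

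**What the plan says.** - **Rule for pre-existing illness (Protocol 8.7).** Illnesses that began before entry and are still ongoing at study start "will not be considered AEs unless they worsen during the treatment period". Otherwise they are entered as medical history.
- **AE collection window (Protocol 8).** AEs and SAEs go into the eCRF "from the time written informed consent is obtained until the end of the follow-up period". The opening of 8.7 has the same end point: AEs are reportable "until the end of the safety follow-up period or the withdrawal of the subject from the study, and any AEs or SAEs reported spontaneously" up to that point. Protocol 5.3.3 lists AE recording at Visit 9 (Week 22).
- **Study periods (Protocol 3.1).** The study has "a 2-week screening period, a 16-week double-blind treatment period, and a 6-week follow-up period at Week 22". Treatment and follow-up are separate phases.
- **Purpose of follow-up (Protocol 3.2).** The visit comes 6 weeks after treatment ends, "which is considered a sufficient duration to evaluate pigmentation recovery and safety of subjects".
- **Analysis definition (SAP 7.12.1, and 2.4.1 in similar words).** TEAEs are "AEs that newly occurred or increased in severity on or after the first dose of study medication". Neither section gives a last day.

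**The concern.** Two rules about the same events have different end points. A new non-serious event in Week 19 is an AE. A non-serious worsening of an existing condition in the same week is not, if the site follows 8.7 to the letter. The SAP would count that worsening as treatment-emergent, but its definition starts from entered AEs, so an event that was never entered cannot reach a TEAE table.

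The class of events is not empty in this trial. Every subject enters with at least one ongoing illness, EPP itself. Exclusion criterion 4 leaves room for AST, ALT and ALP that are raised but below 3 x ULN. Protocol 1.5 reports darkening and enlargement of pre-existing nevi in the Phase I study. Follow-up is also the only scheduled off-drug safety observation for subjects who complete treatment.

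**Working it through.** The documents state no figure for this point, so the check compares windows and does arithmetic on the stated period lengths.

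**Step 1. The windows side by side**

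| Rule | Source | Starts | Ends |
|---|---|---|---|
| AEs recorded in the eCRF | Protocol 8 | consent | end of follow-up |
| AEs reported to the sponsor | Protocol 8.7, opening | consent | end of follow-up, or withdrawal |
| SAEs and hepatic AESIs | Protocol 8.8 | consent | end of follow-up, or withdrawal |
| TEAE, including worsening | SAP 2.4.1, 7.12.1 | first dose | none stated |
| Worsening of a pre-existing illness | Protocol 8.7 | start of treatment period | end of treatment period |

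Only the last row stops at Week 16, and no section extends it. The general AE definition in Protocol 8.1 has no such limit either. Protocol 8 does mention the double-blind treatment period when it classifies AEs as treatment-emergent. There the phrase attaches to dosing and marks a start, so it does not set an end date.

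**Step 2. Length of the gap**

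Inputs: end of treatment at Day 113 and follow-up at Day 155 (Protocol Table 5.1-1); 2, 16 and 6 weeks for the three periods (Protocol 3.1).

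- Follow-up: 155 - 113 = 42 days.
- Planned post-dose time: 16 x 7 + 42 = 112 + 42 = 154 days.
- Share outside the rule: 42/154 = 27.3%. In weeks, 6/22 = 27.3%.
- With the 2 screening weeks, which the wording also leaves out: (2 + 6)/24 = 33% of planned participation. The pre-dose part can be longer, because Protocol 8 lets subjects who travel sign consent weeks before Visit 1.

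**Step 3. What still reaches the database from follow-up**

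- SAEs and hepatic AESIs: reportable (Protocol 8.8).
- Clinically significant laboratory abnormalities: AEs with no period limit (Protocol 6.9.5.2, 8.6). The same holds for vital signs (6.9.2). SAP 7.12.2 also tabulates laboratory values and threshold counts whether or not an AE is entered.
- EPP symptoms: the diary records prodromal symptoms and pain through Visit 9, and the SAP derives a Week 22 value (Table 4, section 5.4.1.1). PROMIS-57 and PGIC are also taken at Visit 9. These are efficacy data.
- Nevi: evaluated at Visit 9 where site staff judge it necessary (Protocol 6.9.4), with their own SAP table (7.12.6).

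**Step 4. What remains**

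The remainder is non-serious clinical worsening of a prior condition with no laboratory or vital-sign route. For these events the missing item is the AE record: severity, causality, treatment required and outcome. The laboratory route is also not complete. Protocol 8.6 has a value that clearly belongs to a diagnosis recorded as that diagnosis, and if the diagnosis is pre-existing, the limit in 8.7 arguably applies again.

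**Step 5. Off-drug time before Week 16**

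Protocol 4.5 lets subjects who stop treatment stay on study. The documents do not say whether their off-drug weeks belong to the treatment period, so the rule is unclear for them too.

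**The case against.** The strongest reply is that the restriction is one literal reading of one sentence. Protocol 8, the general definition in 8.1, the opening of 8.7 and the Visit 9 schedule all point the other way. Sites also work from sponsor eCRF guidelines (Protocol 9.1), which are not among these documents and may not repeat the limit. This stands in part: it cannot be shown that sites will omit these events. But 8.7 is the specific rule for pre-existing illness, and it sends such conditions to medical history. A site that follows it is complying with the protocol. Inconsistent recording between sites is therefore the best case.

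A reader might infer three stronger things, and the documents support none of them.

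- **That off-drug data are not collected.** Step 3 shows that EPP symptoms, laboratory values and vital signs are all taken to Visit 9, and nevi where judged necessary.
- **That the safety comparison is biased in the drug's favour.** The rule is the same in all three blinded arms. A uniform rule could still remove more events from one arm, but only if worsening after stopping differs by arm, and no section reports or predicts rebound. Protocol 1.5 describes only signs that the skin effects reverse. Return of photosensitivity to its entry level is not worsening of a pre-existing illness, so it would not be an AE under amended wording either.
- **That 27% of safety information is lost.** The figure is elapsed time, and most routes for information stay open during it.

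The note on elective hospitalization in 8.7 does count worsening from consent. It governs a different question, whether a pre-planned procedure is an AE, and carries little weight here.

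**Conclusion.** The phrase in 8.7 is wrong as written. It conflicts with the AE window in Protocol 8, with the opening of 8.7 itself and with the SAP's TEAE definition. Followed literally, it leaves non-serious clinical worsening of prior conditions out of the AE and TEAE tables for the 42 follow-up days, and out of the AE listings between consent and first dose. Otherwise it produces uneven recording across sites.

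The size is modest. The window is 27% of planned post-dose time for each of about 102 subjects, but the number of events affected cannot be derived from the documents. No direction of bias is established.

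The conclusion assumes that the treatment period means the 16-week phase named in Protocol 3.1, and that the eCRF guideline does not already override the sentence.

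**What to change.** In Protocol 8.7, replace the closing condition of the sentence on pre-existing illness with: *unless they worsen in severity at any time from informed consent to the end of the follow-up period*. Use the same wording in the eCRF completion guideline.

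The condition should be limited to severity. Both SAP definitions rest on new occurrence or increased severity, so adding frequency would admit events that do not clearly qualify as TEAEs and would create a new mismatch between protocol and SAP.

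Nothing else needs to change. Pre-dose worsening falls into the Baseline class that Protocol 8 already provides, and post-dose worsening meets the existing TEAE definition. Design, sample size and SAP stay as they are. The cost is one phrase in two documents and a few more AE entries, mostly at Visit 9.

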8.9 Pregnancy

If a female subject who has been exposed to the study medication becomes pregnant, the course and outcome of the pregnancy should be monitored and documented. Where possible, if a female partner of a male subject who has been exposed to the study medication becomes pregnant and the subject provides this information, then the pregnancy will be documented based on information provided by the subject.

A pregnancy that occurs in a subject who has been exposed to the study medication must be reported using the same timelines and contact details as an SAE (Section 8.8) by a paper *Pregnancy in a Clinical Study Notification Form*, although pregnancy alone will not be classified as an SAE. If the outcome of the pregnancy or an event occurs during the course of pregnancy that involves an SAE (e.g., a congenital anomaly), then the *Serious Adverse Event (SAE) in a Clinical Study Form* will also be completed.

Subjects who become pregnant while on study should be withdrawn from treatment, as described in Section 4.5.

8.10 Follow-up of Adverse Events

The Investigator should follow up subjects with AEs/SAEs, until the event has resolved or stabilized and any abnormal laboratory values have returned to baseline; or until there is a satisfactory explanation for the changes observed. In the case of death, if possible a pathologist's full report should be supplied.

The reference safety information for this clinical study is the Investigator's Brochure³).

8.11 Overdose

There is no known antidote for MT-7117. Any signs or symptoms of a possible overdose will be treated supportively. In the case of an emergency, standard emergency procedures and supportive medical care will be given.

If the subject takes a dose which is greater or more frequent than that specified in the Protocol (with or without associated symptoms), this overdose is an AE and must be

Mitsubishi Tanabe Pharma Development America, Inc.

reported to the Sponsor or the designee on the AE eCRF.

If the overdose results in AEs that meet serious criteria, the SAE must be reported to Sponsor or the designee immediately or within 24 hours of awareness using the *Serious Adverse Event (SAE) Form in Clinical Study* according to SAE reporting procedures (see Section 8.8).

If the subject experiences any other associated symptoms as a result of the overdose, the Investigator will record this as a separate AE/SAE.

9. DATA COLLECTION AND PROCESSING

9.1 Data Collection

Subject data will be collected on individual eCRFs and will be substantiated by source documents (such as laboratory reports, medical records, or ECGs) at the Investigator site. All relevant data will be transcribed into the eCRF from source documents, entered into the study database directly from source documents, or transferred electronically to the study database. Where no printed or electronic source documents exist, data will be entered directly into the eCRF and the eCRF will be considered the source document.

Subjects will record sunlight exposure time, prodromal symptoms and pain, their severity and their duration on an ongoing basis using a sunlight exposure diary, which includes an electronic patient-reported outcome (PRO) instrument. The instrument will transmit data to a technology service provider database, where it will be stored as electronic source data for efficacy endpoints. To mitigate the potential risk of lost data collection, a printed equivalent of the electronic PRO instrument may be considered to provide emergency back-up in case of device malfunction or loss.

Before the start of the study, the Investigator will complete a Delegation of Responsibility List. The Sponsor or designee will provide training for completion of the eCRF. The eCRF will be completed according to guidelines provided by the Sponsor or its designee in writing, electronically, and/or verbally.

Completed eCRFs will be reviewed by the Study Monitor for the study to ensure data accuracy, completeness, and consistency in accordance with the study monitoring plan and other relevant procedural documents. Any relevant discrepancies found during the eCRF review or during data validation and/or quality assurance reviews of the data by data management or other functions are to be clarified by the Investigator (or his/her designated personnel).

The Investigator or designee must record all required subject data using the previously specified data collection method defined by the Sponsor. An explanation must be documented for any missing data where required. The Investigator must sign and date a declaration on the eCRF attesting to his/her responsibility for the quality of all data recorded, and that the data represents a complete and accurate record of each subject's participation in the study. The data collected in the eCRF will be returned to the Sponsor, and an electronic copy will be retained by the Investigator.

